The second stage will only be conducted if enough external funds are ensured by using the results from the first stage as preliminary data. The second stage would consist of performing 16S rRNA on blood samples to analyze microbial composition in blood, and metabolomic analysis to evaluate the effect of the probiotic on gut-derived metabolites in blood and stools. The hypothesis of this second stage of the project is that the next generation symbiotic will change blood microbial composition as well as the presence and concentration of gut-derived metabolites in blood and stool samples. If relationships exists between changes in body composition, insulin sensitivity, depression, anxiety, or cravings (first stage variables) with blood microbial composition and derived-

metabolites (second stage variables), we could show not only a cause-effect relationship but also the mechanism of action through which the next generation symbiotic acts.

9) Background: Describe the theory or data supporting the objectives of the study and include a bibliography of key references as applicable.

Obesity is a strong risk factor for the development of the majority of the leading causes of death.¹ Recent research has pointed to the gut microbiota as a potential mechanism of action through which body weight can be regulated.² The gut microbiota of people with obesity has a lower alpha diversity³ and lower abundance of *Akkermansia muciniphila*.⁴⁻⁷

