60 participants ages 18-50 that have a BMI between 25.0-40.0 kg/m², who do not also have type 1 or type 2 diabetes mellitus (T1DM or T2DM) will be recruited. Exclusion criteria include: being vegetarian, vegan, carnivore, or keto; pregnancy or planning pregnancy during the study period; lactating women; having a history of inflammatory bowel disease, colon cancer; having been diagnosed with T1DM or T2DM; active cancer; currently participating in a weight loss intervention (dietetic or medication); use of antibiotics, antifungals, or antivirals in the last 3 months; currently taking metformin, GLP-1 agonists, insulin, or fiber supplement; having taken PPI, stimulant laxatives, probiotics, or immunosuppressants in the last month; history of recent (within 30 days) diarrhea illness (including bacterial or viral enteritis or enteric parasitic infection); having a known

hypersensitivity to any component of the study product; having an acute infection or inflammatory condition over the past 4 weeks; having >10% weight variation in the last 6 months; history of bariatric surgery in the past with exemption of laparoscopic band that has been removed.

12) Recruitment Procedure: Describe your recruitment strategies in great detail including how and where the potential participants will be approached and by whom. Will recruitment involve a point of contact on behalf of the study team? Who and how will recruitment material(s) be distributed? Describe precautions that will be taken to minimize the possibility of undue influence or coercion. Include copies of the recruitment emails, flyers, social media post, etc. in your submission as attachments or appendices following the recruitment guidelines.

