visit, depending on the order they enrolled, participants will receive the 3 bottles containing the assigned code. Participants will also be provided with two stool sample collection kits, a 3-day diet record form, a 3-day prescription of antibiotics (500 mg of generic Vancomycin every 8h), date for second appointment, and a start date for the antibiotic regimen. The 3-day antibiotic treatment provided prior to beginning the 12-week synbiotic intervention is given with the intention to increase the number of available bacterial niches (bacterial homes/space) and thus increase the engraftment of the newly ingested bacteria. Although participants will be asked to pay the cost of the generic antibiotic treatment initially (which should have an estimated cost of \$20-25), we will offset the cost of the antibiotic by providing the participants with a \$50 Amazon gift card in their second appointment, so they will not be responsible for any costs to participate in this study. This initial gift card is in addition to their \$100 Amazon gift card provided at the end of the study in appreciation for having taken part in this project. Their insurance will not be charged for any study-related testing; however, they are welcome to (but don't have to) use their insurance to buy the antibiotic. During this first visit, participants will have their 1) first 12h fasted blood collection and will be instructed to 2) fill out a 3 day food log before each stool sample collection, 3) collect a stool sample before the start of the antibiotic regimen, 4) collect a stool sample within 12-48 hours after the last dose of the antibiotic regimen, 5) bring both stool samples and diet records with them to the second appointment and, 6) fast 12 hours prior to the second appointment (refrain from the consumption of all food and liquids, except water). The first appointment is expected to take no greater than 45 minutes.

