For the second visit, participants will meet researchers at the Rickel building. This appointment is expected to take approximately 45 minutes and includes the completion of a DEXA scan, an air displacement plethysmography test (via BOD POD), body weight measurement, the Beck Anxiety and Depression Inventories, the RED-9 questionnaire, and a blood draw. Participants will turn in their first (before antibiotic prescription initiation) and second (after antibiotic prescription completion) stool samples and food logs to researchers. The blood draw will consist on 2 serum separation tubes (10 mL each), 1 EDTA tube (3 mL), and 1 Zymo tube (3 mL). The time to complete each test is approximately as follows: 10 minutes for the blood draw, 10 minutes for the anxiety and depression survey, 20 minutes for the DEXA scan, and 5 minutes for an air displacement plethysmography test. Air displacement plethysmography tests via the BOD POD will be used to measure body fat percentage. Participants will be asked to wear minimal clothes and no shoes for the air displacement plethysmography test. The DEXA scans will be used to measure fat mass, visceral fat, lean mass, and bone mineral density. The DEXA scan uses a two-sided low emission X-ray to quantify lean body mass, fat mass, and bone density. To conduct the test, participants will be asked to void their bladder, remove all metal objects (piercings, rings, etc.) and shoes, and will lay supine on a padded table for approximately 6 minutes while the scanner moves down the length of the participant's body. Measurements will be conducted by a General Electric Certified DEXA Operator ([name] or [name]). Blood samples will be collected using sterile techniques and only by qualified investigators ([name] or [name]). Blood samples will be used to measure fasting glucose, fasting insulin, and HbA1C. Blood will be sampled using venipuncture. The venipuncture samples will be collected using a traditional blood draw needle to extract blood from a vein in the antecubital region of the arm. Two 10 mL vials of blood will be collected, centrifuged to separate the serum. One of those tubes will be stored in a -80°C freezer in the Exercise Physiology Laboratory (Rickel 259) whereas the other will be transported to BioReference for fasting glucose and insulin analysis. The 3 mL for EDTA analysis will also be transported to BioReference for HbA1C analysis. The Zymo collection tube (3 mL) will be stored at the Rickel 259 building. All blood collection vials and plasma/serum containers will be

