
labeled using participant numbers (deidentified) for participant privacy. The leftover blood samples will be stored in the laboratory for 10 years from date of collection at which point they will be discarded as biohazard waste. Participants agree to allow their deidentified samples to be used for future research by signing the informed consent. These procedures have been approved by the TCU Institutional Biosafety Committee (IBC Protocol). At the end of the second appointment, participants will be provided with the 12 weeks of the probiotic+prebiotic supplement. Each person will receive 3 bottles (one per month) with the three of them having the same ID, this same ID will be used to identify all questionnaires and samples obtained from that person. This ID will also be different between each participant. Participants will also be instructed to 1) record everything they eat for 72 hours before stool sample collection, 2) collect a stool sample within 24 hours of finishing the last dose of the intervention, 3) bring the stool sample, diet record, and remnant of their supplement or placebo with them to the third appointment, and 4) fast 12 hours prior to the third appointment (refrain from the consumption of all food and liquids, except water).

The third and final appointment is expected to also take approximately 45 minutes and will include a replication of all tests conducted in the second appointment (completion of a DEXA scan, an air displacement plethysmography test [via BOD POD], body weight measurement, the Beck Anxiety and Depression Inventories, the RED-9 questionnaire, and a blood draw [consisting on 2 serum separation tubes of 10 mL each, 1 EDTA tube of 3.5 mL, and 1 Zymo tube of 3mL]). Participants will turn in their third and final stool sample, as well as the remnant of their supplements or placebo for analysis of adherence and compliance. Participants will receive a \$100 Amazon gift card at the end of the study in compensation for their time. After all stool samples have been collected, they will be sent in the same batch to the Alkek Center for Metagenomics and Microbiome Research (CMMR) at Baylor College of Medicine in Houston for posterior whole genome sequencing analysis.

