If participants withdraw from their study the data collected up to that point will remain available for research purposes with the intention to use intent to treat analysis. Blood and stool samples will be stored in [name] lab located within the Rickel building room 259. For the first stage of the project, blood samples will be analyzed at [name] lab room 259. Once the Nutritional Sciences Department laboratory has been finalized, samples will be transferred to the Nutritional Sciences Department and further storage and analyses could take place here (BASS, room 1203). If enough funds become available to perform the second stage of the study, blood and stool samples (which will be identified by fabricated ID) will be sent to Baylor College of Medicine and to Metabolon for posterior 16S rRNA/WMS and mass spectrometry analyses, respectively. For statistical analysis of the first stage, two sample T-tests will be used to compare within (pre- versus post- values on each group) and between-group (placebo versus probiotic) differences in body composition, adherence, metabolic, dietary, and psychological variables. SPSS will be used for statistical analysis. A p value <0.05 will be considered as statistically significant. Dietetic variables collected via the NCI Automated Self-Administered 24-hour Dietary Assessment Tool including protein, carbohydrate, fat, and fiber will be controlled statistically in the case that significant intra-individual or between-group differences are observed.

20) Check List for the Items That Need to be Submitted: Please submit protocol and consent documents separately in MS word, supplemental documents (interview guides, surveys, recruitment materials etc. can be submitted as separate pdfs) before submitting the materials electronically to the IRB. To prevent any delay in the approval of your protocol, use the most recent template for the protocol, consent document, and HIPAA form by downloading them from <https://research.tcu.edu/research-compliance/irb/irb-forms-templates/> each time you prepare your materials.

a. Protocol	X
b. Consent document	X
c. Protecting Human Research Participants Training complete for each investigator	X
d. Recruitment flyers, letters, ads, etc.	X
e. Questionnaires or other documents utilized in screening and data collection	X

Principal Investigator Assurance

21) By signing below, I certify to the following:

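### The between-arm t-test does not say whether it uses week-12 values or changes, and no outcome is adjusted for its own visit 2 value

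*Combined protocol and SAP*

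**What the plan says.** Section 19 (Data Analyses) is the only analysis text for the first stage. It states that "two sample T-tests will be used to compare within (pre- versus post- values on each group) and between-group (placebo versus probiotic) differences", applied to "differences in body composition, adherence, metabolic, dietary, and psychological variables". The pre-versus-post wording qualifies the within-group comparison only. The between-group comparison is qualified only by the names of the two arms. The one adjustment mentioned concerns dietary intake, and only if significant differences in it are seen.

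Section 14 (Study Procedures) shows that the same outcomes are measured before and after supplementation. The second visit includes DEXA, BOD POD, "body weight measurement, the Beck Anxiety and Depression Inventories, the RED-9 questionnaire, and a blood draw". The third visit "will include a replication of all tests conducted in the second appointment". Adherence is the exception: it is judged at the third visit from "the remnant of their supplements or placebo for analysis of adherence and compliance", so it has no baseline.

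Section 8 (Purpose) refers to changes in the first-stage variables, but as quantities to be related to second-stage measures. It does not define the between-arm comparison. Section 11 plans "60 participants ages 18-50". The documents give no effect size, SD, power or dropout rate behind that number.

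**The concern.** A statistician following Section 19 could run the between-arm test on visit 3 values or on changes and be within the plan either way. In a trial of 60 the two can give very different power, and even different conclusions, from the same data. A choice that is open until both results can be seen also weakens the nominal 5% level.

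Neither reading makes best use of the visit 2 value. A comparison of week-12 values ignores it. A change score subtracts it in full, which over-corrects whenever the correlation is below 1 (with equal SDs). If the arms differ at baseline by chance, the two tests err in opposite directions.

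**Working it through.** **Inputs from the documents.** Total 60 (Section 11); significance at p < 0.05 (Section 19); the same measures at visits 2 and 3 (Section 14). There is no stated power calculation to reproduce.

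**Assumptions, not in the documents.** 1:1 allocation with 30 per arm and no dropout; two-sided testing; equal SDs at both visits; pre-post correlation r from 0.3 to 0.95.

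**Formulas.** In units of the outcome SD, the SD that drives each between-arm comparison is:
- week-12 values: 1
- change: √(2(1−r))
- baseline-adjusted (ANCOVA): √(1−r²), with variance multiplied by about 57/56 because the slope is estimated from 60 people

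The standard error is that SD × √(2/30) = SD × 0.258. Power uses the noncentral t distribution with 58, 58 and 57 degrees of freedom.

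| r | Detectable difference at 80% power, SD (week-12 / change / adjusted) | Power for 0.5 SD (week-12 / change / adjusted) |
|---|---|---|
| 0.3 | 0.736 / 0.870 / 0.708 | 48% / 36% / 51% |
| 0.5 | 0.736 / 0.736 / 0.643 | 48% / 48% / 59% |
| 0.7 | 0.736 / 0.570 / 0.530 | 48% / 69% / 75% |
| 0.8 | 0.736 / 0.465 / 0.445 | 48% / 85% / 88% |
| 0.95 | 0.736 / 0.233 / 0.232 | 48% / >99% / >99% |

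**Sample-size equivalent of adjustment**, at r = 0.3 / 0.5 / 0.7 / 0.8 / 0.95:
- against week-12 values, 1/(1−r²) × 56/57 = 1.08 / 1.31 / 1.93 / 2.73 / 10.1
- against change, 2(1−r)/(1−r²) × 56/57 = 1.51 / 1.31 / 1.16 / 1.09 / 1.01

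**Weight, as an illustration** (assumed SD 15 kg, true effect 2 kg). On week-12 values the standard error is 15 × 0.258 = 3.87 kg and power is 8%. At r = 0.98 the SD of change is 15 × √0.04 = 3 kg, the standard error is 0.77 kg, and power is 72% for change and 72% adjusted. The figure depends strongly on r: both methods give 36% at r = 0.95 and 95% at r = 0.99.

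**Open choice.** In simulations under no effect (100,000 trials per r), rejecting when either t-test has p < 0.05 gave a type I error of 0.091, 0.095, 0.096 and 0.097 at r = 0.5, 0.7, 0.8 and 0.95. The adjusted model gave 0.050.

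**Chance imbalance.** The standard error of the visit 2 difference is √(2/30) = 0.258 SD, so a difference of 0.3 SD or more in either direction has probability 0.245. Given a 0.3 SD difference and r = 0.6, the week-12 comparison is shifted by 0.3 × 0.6 = +0.18 SD and the change comparison by 0.3 × (0.6 − 1) = −0.12 SD. The adjusted model removes the shift in expectation.

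**The case against.** The strongest reply is that either t-test is valid under randomisation, that the first stage is described as exploratory and as preliminary data for funding, and that the wording leans towards changes: Section 8 hypothesises decreases and increases. On that reading the dramatic contrasts (8% against 72%, or ten times the sample size) disappear. What remains is a gain of 1.31 times at r = 0.5, falling to 1.01 at r = 0.95. The inflated type I error needs someone to pick the result after seeing both. Nothing in the documents suggests that this is intended, and one sentence naming either t-test would remove it.

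Much of this is fair on size. The large losses do belong to the week-12 reading and to highly correlated outcomes, and 9-10% is a worst case. It does not remove the point. Section 19 does not say that changes are meant. Changes are the poorest of the three choices when r is low (36% power at r = 0.3), and week-12 values are poor when r is high. Adjustment is best or essentially tied across the range, so one rule serves outcomes as different as weight and questionnaire scores.

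A further objection is that the baseline itself is not clear-cut. In Section 14 the first-visit text has the bottles handed out at that visit, while the second-visit text has them provided at its end. These statements must be reconciled. The second-visit text places supplementation after the visit 2 measurements, which is what the proposed model relies on.

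**Conclusion.** The concern holds. The between-arm quantity is not defined, and no outcome is adjusted for a pre-supplement value that the trial already collects. This is under-specification and lost efficiency, not an invalid test.

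For moderately correlated outcomes (r = 0.5 to 0.8), adjustment raises power for a 0.5 SD effect from 48% to 59-88% compared with week-12 values, and by 3 to 11 percentage points compared with changes. For very stable measures it adds essentially nothing over changes but rules out the costly week-12 comparison. All these figures rest on 30 per arm, equal SDs and an assumed r; dropout would lower all the power figures. The point does not apply to adherence. The change should be made before the data are analysed.

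**What to change.** In Section 19, for each continuous outcome with a pre-supplement value, replace the between-group t-test with a linear model: visit 3 value = arm + visit 2 value. Report the adjusted mean difference with its 95% confidence interval as the between-arm result.

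Also state:
- that visit 2 is the baseline, as the last measurement before supplementation and the only pre-supplement visit with DEXA, BOD POD and the questionnaires (weight and fasting blood also exist at visit 1), once the two statements on when bottles are handed out are reconciled;
- which pre-supplement dietary record is the baseline for dietary variables, since Section 14 tells participants to "fill out a 3 day food log before each stool sample collection" and two stool samples precede supplementation, and how those logs relate to the 24-hour dietary tool named in Section 19;
- whether the baseline-adjusted model without dietary covariates is the main result, so that the conditional dietary adjustment does not reopen the choice;
- that adherence keeps a simple two-sample comparison.

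The Figure 1 caption gives the intervention as four months where the text says 12 weeks; these should be reconciled so that the timing of visit 3 is unambiguous.

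The cost is a few sentences and one degree of freedom. It is a standard SPSS procedure and needs no new data.

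### Section 19 names two-sample t-tests for within-group pre-post comparisons of the same participants; the paired t-test should be named

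*Combined protocol and SAP*

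**What the plan says.** The statistical plan for the first stage is a few sentences in Section 19 (Data Analyses). The sentence on tests reads: "two sample T-tests will be used to compare within (pre- versus post- values on each group) and between-group (placebo versus probiotic) differences". It covers body composition, adherence, metabolic, dietary and psychological variables. SPSS is the software, without a named procedure, and significance is p < 0.05. Nutrient intakes are then to be "controlled statistically in the case that significant intra-individual or between-group differences are observed".

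Section 14 (Study Procedures) shows how the data arise. The third visit "will include a replication of all tests conducted in the second appointment", and of the bottle code it says that "this same ID will be used to identify all questionnaires and samples obtained from that person". Adherence is assessed once, at the third visit, from the "remnant of their supplements or placebo for analysis of adherence and compliance".

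No paired t-test, signed-rank test, change-score analysis or repeated-measures model appears in the documents. The word 'paired' occurs only as a sequencing term in the 16S methods.

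**The concern.** The parenthesis in Section 19 defines the within-group comparison as pre against post in each group. Those are two measurements on one set of people, whereas a two-sample t-test treats them as two unrelated sets. The point estimate of mean change is the same, but the standard error ignores the pre-post correlation. For measures such as weight, fat mass or a questionnaire score, that correlation can be expected to be positive, so the standard error is too large and the confidence interval too wide.

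At stake is the reported precision and significance of change within each arm. The test also feeds the dietary-adjustment rule, because a significant intra-individual difference is one of its two triggers. Adherence has no pre-value, so the within-group half of the sentence cannot apply to it.

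**Working it through.** There is no stated power, effect size, SD or correlation in the documents, so there is no figure of the plan's own to reproduce. The check shows the consequence over a range of assumptions.

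**Inputs from the documents:** 60 participants (Sections 8 and 11); blocked randomization meant to balance the groups, ratio not stated (Section 14); p < 0.05, sidedness not stated (Section 19).

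**Assumptions:** 30 per arm, two-sided testing, equal pre and post variances, normal data, no missing values, and r = 0.3, 0.5, 0.7 or 0.8.

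**Standard error of mean change in one arm**
- As written: SD × sqrt(2/n)
- Paired: SD × sqrt(2(1 − r)/n)
- Ratio: 1/sqrt(1 − r). At r = 0.5 this is 1/sqrt(0.5) = 1.41.

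**95% CI half-width, n = 30**
- As written, 58 df: 2.002 × sqrt(2/30) = 0.517 SD at every r.
- Paired, 29 df: 2.045 × sqrt(2(1 − r)/30). At r = 0.5 this is 2.045 × 0.1826 = 0.373 SD.

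**Power and type I error.** A paired t-test with n = 30 has 80% power when the mean change is 0.529 SD of the differences (noncentral t). In units of the raw SD this is 0.529 × sqrt(2(1 − r)). Both tests were applied to the same simulated bivariate normal data, 400,000 datasets per value of r; a separate run of 200,000 per value agreed.

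| r | SE ratio | Half-width, written (SD) | Half-width, paired (SD) | Power, written (paired = 80%) | Type I error, written |
|---|---|---|---|---|---|
| 0.3 | 1.20 | 0.517 | 0.442 | 69% | 0.020 |
| 0.5 | 1.41 | 0.517 | 0.373 | 53% | 0.007 |
| 0.7 | 1.83 | 0.517 | 0.289 | 25% | 0.0008 |
| 0.8 | 2.24 | 0.517 | 0.236 | 9% | below 0.0001 |

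The paired test held its type I error at about 0.05 throughout. The written test falls below its nominal level, so the error is one of missed change and not of false claims.

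**The case against.** The strongest reply is that this is a slip of wording. Section 19 never says independent or unpaired, it defines the comparison as pre versus post, and it goes on to speak of intra-individual differences. The authors may well have meant SPSS's paired-samples procedure. The trial is also placebo-controlled: its hypotheses concern the synbiotic's effect, which within-arm tests do not establish. All of this stands, and it limits the weight of the point. It does not remove it, because one label is given to two comparisons that need different tests, and it fits only one of them.

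Three stronger readings are tempting, and the documents do not support them.

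- **That the error damages the treatment comparison.** A two-sample t-test is a suitable test for two independent arms, and positive pre-post correlation makes the within-arm test too cautious, not too liberal.
- **That it harms the arm comparison through the dietary rule.** The choice of test can change whether the intra-individual trigger fires, but more firing is not clearly better. With no true dietary change, 30 per arm, and the between-arm test made on change, the rule fires for a single nutrient in about 5% to 6% of trials as written and about 11% to 12% with the paired test, at r = 0.5 to 0.8. A between-group difference can also trigger it.
- **That visit 2 is simply the 'pre' value for everything.** Section 14 schedules a fasted blood draw at the first visit as well. Participants also hand in "first (before antibiotic prescription initiation) and second (after antibiotic prescription completion) stool samples and food logs to researchers", while Section 19 says the nutrient data come from the NCI 24-hour tool; the documents do not link that tool to the logs. Which measurement is 'pre' cannot be settled from the text.

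One caution applies to the remedy. A paired test uses only participants with both values, while Section 19 states an intention to analyse by intent to treat. The within-arm summary must be kept distinct from that analysis.

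**Conclusion.** The point holds. As written, Section 19 specifies the wrong test for within-group pre-post change, and the plan names no other. If it is followed literally, the within-arm standard error is 1.20 to 2.24 times too large for r between 0.3 and 0.8, and a change that a paired test would detect with 80% power is detected with 69% down to 9%. The SE ratio depends on r and on equal variances; the power figures also depend on 30 per arm and two-sided 0.05. None of these is given in the documents apart from the 0.05 threshold.

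The consequence is conservative and limited to within-arm results. The between-arm test is not directly affected. An effect through the dietary-adjustment rule is possible, but harm to the arm comparison is not shown. The point should be fixed because the specification is wrong and the correction is nearly free, not because it threatens the trial's main conclusion.

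**What to change.** Replace the test sentence in Section 19 with:

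> Within-arm pre-post change will be reported as mean change with 95% CI from the paired-samples t-test, stating the number of participants with both values; any test of intra-individual dietary change uses the same test. Placebo and probiotic will be compared with the two-sample t-test for independent groups, and conclusions about the synbiotic rest on this between-arm comparison. Adherence is compared between arms only.

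Add that the paired within-arm summary is descriptive and separate from the intent-to-treat between-arm analysis.

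The cost is a few sentences, settled before the allocation code is merged with the data. No new data are needed: the shared ID already links each person's values, and the paired-samples t-test is standard in SPSS. The edit does not decide how withdrawals enter the intent-to-treat analysis, whether the between-arm test uses post-values or changes, or which measurement counts as 'pre'.
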